Clinical assessments and sample collection will occur at regularly scheduled visits through Week 48 with telephone follow-up conducted in the interim. If a subject has not recovered B cells by Week 48, B cell studies will be conducted quarterly until recovery is documented or for 2 years after initial treatment (whichever occurs first). Recovery is defined as the time point at which B cells recover to within 10% of baseline levels; if a baseline value is not available then recovery is defined as a B cell level of at least 90% of the lower limit of

normal. During this quarterly monitoring period of B cell recovery, AEs and SAEs will be assessed, providing the subject has not withdrawn consent, to capture any infectious event \geq Grade 3 using the National Cancer Institute - Common Terminology Criteria for Adverse Events (NCI-CTCAE). No additional study-related data will be collected. Vital status on all subjects will be evaluated \geq 2 years after randomization.

The primary efficacy endpoint is the change in 6MWD from baseline to 24 weeks after treatment initiation. Hemodynamic measures will be assessed at baseline and Week 24, contributing to the understanding of the relationship between PVR and clinical endpoints. Initiation of new PAH therapy due to disease worsening prior to Week 24 will prompt an endpoint visit and right heart catheterization prior to initiation of the new therapy. B cell recovery for all will be monitored by serial assessments of B cell counts as determined by flow cytometry.

The total duration of the study is anticipated to be approximately 8 years.

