3.3.3 Subject Withdrawal from the Study

When a subject is withdrawn from the study after initiating treatment but prior to B cell follow-up, protocol-specified treatment requirements are discontinued and study-related visits, exams, procedures, assessments, tests and data collection are terminated after completion of an Early Endpoint Visit as detailed in Section 6.5.5, *Early Endpoint Visit*. However, individual subjects will be withdrawn from the protocol under the following conditions:

1. The subject withdraws consent.
2. The investigator or DAIT/NIAID believes it is in the best interest of the subject.
3. The study is terminated.

Subjects who are lost to follow-up will also be regarded as withdrawn from the protocol.

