7.3.3. Clinical Worsening

Endpoint: Assessment of time to clinical worsening, censored at 48 weeks, will be defined as first occurrence of the following: death, hospitalization for SSc-PAH, lung transplantation, atrial septostomy, addition of other PAH therapeutic agents, or worsening of 6MWD by > 20% and

an increase in functional class. The components of clinical worsening will be assessed as follows.

- a. Death: Date of death will be collected on the Post-Study Follow-Up/Week 104 Vital Status CRF page.
- b. Hospitalization for SSc-PAH: Date of hospitalization for SSc-PAH will be collected on the Serious Adverse Event CRF page and determined from SAEs that had seriousness criteria of “Required hospitalization or prolongation of existing hospitalization” and that were marked as being possibly, probably, or definitely related to worsening disease on the Adverse Events CRF page. Time to the event will be derived from the date that the AE became serious. If a subject has multiple hospitalizations for SSc-PAH, then the first date will be used.
 - i. A second clinical worsening endpoint will be similarly defined except that “hospitalizations for SSc-PAH” will be evaluated by a blinded review panel to exclude those events relating only to a subject’s SSc and not PAH.
- c. Lung transplantation: Date of lung transplant will be collected on the Initiation of New PAH Medications and Therapy CRF page.
- d. Atrial septostomy: Date of atrial septostomy will be collected on the Initiation of New PAH Medications and Therapy CRF page.
- e. Addition of other PAH therapeutic agents: Date of new medications or doses of PAH medications changed for the treatment of PAH will be collected on the Initiation of New PAH Medications and Therapy CRF page.

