- f. Worsening of 6MWD by > 20% and an increase in functional class: The 6MWD and the NYHA Functional Class Assessment will be performed at Screening and Weeks 4, 12, 24, 36, and 48; they may also be performed at an unscheduled visit. Data for the 6MWD will be collected on the 6-Minute Walk Test CRF page and data on functional class will be collected on the NYHA Functional Class Assessment CRF. The first date at which the 6MWD has decreased by >20% from the Screening walk distance and the NYHA Functional Class Assessment has increased a class from Screening will be recorded. If a subject’s 6MWD decreased from Screening by more than 20% and a repeat 6MWD was performed, then the better of the two values will be used in the analysis. If a subject is NYHA Class IV at baseline, then only a decrease of 20% in the 6MWD will be required.

Time to clinical worsening will be defined as the first date that meets any of the above criteria and will be calculated in study days as: date of first event – date of randomization. If a subject does not experience a relevant event by Week 48 or if the date of death is after the 48 week follow-up period, then time to clinical worsening will equal the duration of follow-up in the main study for that subject. Appropriate censor variables will be defined to indicate whether the time-to variable represents an event time or a censor time.

Analysis: Time to clinical worsening and type of clinical worsening reached will be summarized by treatment group and overall. Kaplan-Meier curves, including 95% confidence intervals, will be created for each treatment arm and will be compared using the log-rank test. A Cox proportional hazards model may be fit to assess the effect of treatment on time to clinical worsening, if appropriate. Additional covariates may be added to the model as appropriate. Analyses will be run using the definition of hospitalization of SSc-PAH as defined in both point B and B.i above.

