8.2. Adverse Events

All AEs will be classified by system organ class (SOC) and preferred term, according to a standardized thesaurus (Medical Dictionary for Regulatory Activities [MedDRA] version 13.1). The severity of AEs will be classified using the National Cancer Institute's (NCI's) Common Toxicity Criteria for Adverse Events (CTCAE) version. Each AE is entered on the electronic case report form (eCRF) once at the highest severity. As such, no additional data manipulation is needed to identify events.

Adverse events NCI-CTCAE grade 2 and above will be collected from the time the subject signs the informed consent until he/she initiates study intervention or until he/she is determined to be ineligible to receive study intervention, if the investigator determines that the adverse event is related to a study-mandated procedure, treatment, or change in treatment.

For all participants, adverse events NCI-CTCAE grade 2 and above will be collected from the time of initiation of study intervention (i.e., the administration of the first dose of study drug/study drug) until he/she completes study participation or until 30 days after he/she prematurely withdraws (without withdrawing consent) or is withdrawn from the study. During the quarterly monitoring period of the study, only NCI-CTCAE grade 3 and higher infections are collected on the adverse events CRF page. Grade 3 and higher infections that occur during the quarterly monitoring period will be listed separately and will not be included in data tabulations, unless otherwise specified.

Treatment-emergent AEs will be identified as those with an onset date on or after the first dose of study medication. If the start of the AE in relation to the start of study medication cannot be established (e.g., the start date for the AE is missing), then the AE will be considered treatment-emergent. All data tabulations will be of only treatment-emergent events unless otherwise specified; non-treatment-emergent AEs will be listed.

An overall summary table will be developed to report the number of events and the number and percentage of subjects having at least one event in the following categories:

- AEs
- AEs requiring 24-hour reporting to the sponsor
- AEs indicated as serious
- AEs that lead to study drug discontinuation
- AEs with an outcome of death
- AEs by relationship to a study drug
- AEs reported by maximum severity

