8.3.2. Deaths

Any death that occurs while a subject is active in the main study (up to Week 48) will be collected and reported as a SAE, and any death that occurs after main study completion will only be reported as a SAE if the subject is active in quarterly monitoring for B cells and if the cause of death is determined to be a Grade 3 or higher infection. Additionally, an assessment of vital status approximately two years post randomization will be conducted via telephone or

review of public records or health registries (to which the subject has consented to share this data). Any deaths discovered from this review will be recorded on the Post-Study Follow-Up/ Week 104 Vital Status CRF page.

Treatment-related mortality will be defined as death occurring after randomization and before Week 48, and possibly, probably, or definitely resulting from study treatment. Treatment-related mortality can only be assessed if a death was reported as a SAE; relationship to study treatment was not collected for deaths recorded on the Post-Study Follow-Up/ Week 104 Vital Status CRF page. As such, treatment-related mortality will be summarized at Week 48.

All-cause mortality, defined as any death occurring after randomization, will be summarized at Week 48 and Week 104.

In addition, time to all-cause mortality will be defined as the number of months post-randomization until death from any cause. If death does not occur during the post-randomization study period (up to Week 104), then time to all-cause mortality will be set equal to Week 104 or the day of the Week 104 vital status telephone call, whichever occurred first. Appropriate censor variables will be defined to indicate whether the time-to variables represent event times or a censor times. Kaplan-Meier survival curves from each treatment arm will be compared using the log-rank test.

Separate displays listing and summarizing death, including time to death and cause of death, will also be created

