²⁴ Required only if the unscheduled visit is due to an increase in SSc-PAH disease activity; see Section 6.5.8, *Unscheduled Visit* for further details.

²⁵ Hemoglobin, platelets, lymphocytes, neutrophils, and bands results from a hematology specimen drawn within 24 hours of the infusion must be reviewed prior to initiating the study drug infusion (see Section 5.3.6, *Criteria for Withholding Rituximab Infusion*).

²⁶ A member of the research staff will obtain verbal consent to conduct an assessment of vital status and treatment satisfaction approximately two years post randomization for each subject. If the subject cannot be reached, a review of public records or health registries should be completed.

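### SAP 7.3.3 counts a death after early exit as a clinical-worsening event but censors a surviving leaver at exit, so who stays at risk depends on a later death

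*SAP*

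**What the plan says.** SAP 7.3.3(a), on the death component: "Date of death will be collected on the Post-Study Follow-Up/Week 104 Vital Status CRF page". A death is set aside only "if the date of death is after the 48 week follow-up period". Nothing requires the subject to have been in the study when it occurred. For everyone without an event, "then time to clinical worsening will equal the duration of follow-up in the main study for that subject".

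The SAP does not define that duration for an early leaver. Protocol 3.3.3 supplies the natural reading: on withdrawal, study visits, "tests and data collection are terminated after completion of an Early Endpoint Visit". Adverse events, which are the source for hospitalizations, continue a little longer, "until 30 days after he/she prematurely withdraws (without withdrawing consent) or is withdrawn from the study" (SAP 8.2).

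Deaths after exit will often be found. Protocol 3.1 states "Vital status on all subjects will be evaluated" about two years after randomization, and the schedule of events adds "If the subject cannot be reached, a review of public records or health registries should be completed".

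SAP 7.3.3 plans Kaplan-Meier curves by arm and a log-rank test, with a Cox model if appropriate. For time to all-cause mortality, SAP 8.3.2 uses a different rule: survivors run to Week 104 or the vital status call, whichever comes first. SAP Section 11 lists only the functional-class wording as a change for clinical worsening.

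**The concern.** Kaplan-Meier and log-rank methods need a subject's presence in the risk set at time t to be decided by what has happened up to t. Here it is not. Take a subject who leaves event-free at Week 10. If that subject dies at Week 40, he or she is at risk for 30 more weeks and then has an event. If he or she lives, follow-up stops at Week 10. The two histories are identical at Week 10 and are treated differently because of what happens later.

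Between exit and Week 48 the retained leavers are, by construction, all going to die. They add deaths to the numerator, while the survivors who should balance them are missing from the denominator. What is at stake is the reported worsening rate in each arm and, if early exit differs by arm, the comparison between arms.

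**Working it through.** The documents give no event rate, event count or power for this endpoint, so there is no stated figure to reproduce.

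**Inputs**
- 30 subjects per arm (Protocol synopsis).
- Exit: 20% by Week 48, range 10 to 30%. The 20% is the dropout allowance in Protocol 8.1, borrowed from the Week 24 endpoint. As a check, 24 completers per arm, a 33 m difference and an SD of 58 m give 50.4% power against the stated 50%.
- One-year survival: 81% (one cohort cited in Protocol 1.1), with 90% and 95% as assumed alternatives.
- Composite rate by Week 48: assumed 20%, 35% and 50%.
- Constant hazards, with exit unrelated to risk in the base case.

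**Weekly hazards at 81% survival, 35% composite, 20% exit**
- Death: λd = −ln(0.81)/52.18 = 0.00404
- Any component: λ = −ln(0.65)/48 = 0.00897
- Exit: λc = −ln(0.80)/48 = 0.00465

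**Hazard that the SAP rule estimates**
- On study and event-free at t: S(t) = exp(−(λ+λc)t).
- Left event-free and alive at t: A(t) = ∫ from 0 to t of λc·exp(−(λ+λc)u)·exp(−λd(t−u)) du.
- Of A(t), the rule keeps at risk only those who will die by Week 48, a fraction 1 − exp(−λd(48−t)).
- h(t) = [λS(t) + λd·A(t)] / [S(t) + A(t)·(1 − exp(−λd(48−t)))].
- Estimated Week 48 rate = 1 − exp(−∫ from 0 to 48 of h(t) dt).

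Under exit-censoring the A(t) terms disappear and h(t) = λ, which returns 35.0%.

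**Direction.** Among retained leavers the apparent hazard is λd/(1 − exp(−λd(48−t))). This always exceeds 1/(48−t), and so is at least 1/48 = 0.0208 per week, against λ = 0.00897. With exit unrelated to risk, the pooled estimate must rise.

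**Size at 20% exit and a 35% composite**

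| One-year survival | Censor all at exit | SAP rule | Carry known survivors to Week 48 | Post-exit deaths per 30 |
|---|---|---|---|---|
| 81% | 35.0% | 36.4% | 33.3% | 0.49 |
| 90% | 35.0% | 35.7% | 32.5% | 0.26 |
| 95% | 35.0% | 35.4% | 32.0% | 0.13 |

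Simulation with 400,000 subjects per setting agrees to within about 0.1 point; its excesses at 95% survival were 0.3 to 0.4 points. Over 54 settings (3 survival × 3 composite × 3 exit levels × post-exit hazard unchanged or doubled) the SAP rule was above both alternatives every time. With unchanged hazard it exceeded the true rate by 0.1 to 2.9 points.

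**Comparison of arms.** Equal arms of 30, 81% survival, 35% composite, 6,000 replicates, nominal 5% test (Monte Carlo standard error √(0.05·0.95/6000) = 0.3 points):
- Exit 20% in both arms: type I error 4.7% under the SAP rule, 4.9% under exit-censoring.
- Exit 10% versus 30%: 5.5% under the SAP rule, 5.4% under exit-censoring. The mean z moves by about +0.10 toward more events in the arm with more exits, against −0.01 under exit-censoring.

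**The case against.** **The effect is small.** With 30 per arm the Kaplan-Meier standard error is about √(0.35·0.65/30) = 8.7 points, against a base-case excess of at most 1.4. Exposure may be lower still. A subject who exits because PAH therapy changed already has an event. One who stops infusions without needing prohibited PAH therapy keeps all visits. The vital status review depends on consent. All of this stands.

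**The protocol defines the endpoint as first occurrence, including death, censored at 48 weeks, with no on-study condition.** Discarding a confirmed death at Week 40 is therefore debatable. This also stands, and it is why a sensitivity analysis counting such deaths belongs in the plan. It does not rescue the mixture: if deaths count to Week 48, survivors with known status must also be carried there.

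**The duration of follow-up is undefined for leavers, so another reading is possible.** True, but no passage in either document supplies one, and SAP 8.3.2 shows a consistent rule being written out for mortality.

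**Main-study deaths.** A reader might infer that they are lost from the composite, because 7.3.3(a) names only the vital status page while 8.3.2 says "Any death that occurs while a subject is active in the main study (up to Week 48) will be collected and reported as a SAE". The documents do not support that. Neither section says main-study deaths are kept off the vital status page, which is meant to cover all subjects. It is an ambiguity of source that needs one clarifying line.

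**Conclusion.** The rule is internally inconsistent as written and should be corrected. Its size is modest: about 0.3 to 1.4 points over exit-censoring at 20% exit and a 35% composite, from 0.1 to 0.5 post-exit deaths per arm. This rests on constant hazards, exit unrelated to risk, and assumed composite and exit rates. The endpoint is secondary, with p-values presented descriptively (SAP 7.3), and the primary analysis is untouched.

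Two stronger readings are not supported:
- **That the worsening rate is always overstated relative to the truth.** The SAP rule exceeds both consistent rules in every setting run, but the truth is another matter. After exit, apart from the 30-day adverse event window, non-fatal components go unseen. If leavers are sicker (all hazards doubled after exit), the net error against the true rate runs from −3.5 to +2.6 points.
- **That the treatment comparison is materially biased.** With equal exit the log-rank test keeps its level. Even at 10% versus 30% exit, its error rate cannot be told apart from that of exit-censoring, although z drifts slightly. Nothing in the documents points to such an imbalance.

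**What to change.** In SAP 7.3.3:

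1. State that event-free subjects are censored at main-study exit, and define exit as the last main-study assessment, or the end of the 30-day post-withdrawal window if SAEs in that window are counted. State that a death is an event only if it occurs on or before that date. Later deaths remain in the all-cause mortality analysis of 8.3.2.
2. Add a sensitivity analysis that counts all deaths to Week 48 and carries every subject with known vital status to Week 48 or the last date known alive.
3. In 7.3.3(a), name both the SAE page and the vital status page as sources of death dates, to agree with 8.3.2.

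The cost is wording and one extra analysis, with no new data. Typically fewer than one post-exit death per arm leaves the main composite analysis. Exit-censoring has its own bias if exit is informative. The sensitivity analysis addresses this, but it tends to understate the composite because non-fatal events after exit are not observed (33.3% against 35.0% in the 81% survival case). The two results should be read together.

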7.3.4. Addition of PAH medications

Endpoint: New medications or doses of PAH medications changed for the treatment of PAH will be collected on the Initiation of New PAH Medications and Therapy CRF page. Date of the

new or modified medication along with reason for the change will be collected for the first time a PAH medication is modified or added.

Indicator variables for new or modified PAH therapeutic agents will be derived for two time points: prior to Week 24 and after Week 24. Time to the addition or modification of PAH medications will be defined in study days as: date of the first time a PAH medication is modified or added – date of randomization.

Analysis: The number and proportion of subjects who changed or added PAH therapeutic agents prior to Week 24 and after Week 24 will be summarized by treatment group and overall, along with the reason for changes to the background PAH medications. Time (in days) to the addition or modification of PAH medications will also be summarized by treatment group and overall.

Kaplan-Meier curves, including 95% confidence intervals, will be created for each treatment arm and will be compared using the log-rank test.

7.3.5. Quality of Life: SF-36

Endpoint: Change in quality of life as determined by the Short Form Health Survey (SF-36) will be assessed at Baseline and Weeks 24 and 48. Data for the SF-36 will be captured on the Short Form – 36 Health Survey CRF page. The SF-36 is a 36-item, patient-reported survey of patient health. Higher scores indicate better outcomes while lower scores indicate more disability.

The following SF-36 scale scores will be calculated: Physical Functioning, Role-Physical, Bodily Pain, General Health, Vitality, Social Functioning, Role-Emotional, and Mental Health. From these scale scores, two summary scores that aggregate measures will be created. The Physical Component Score is comprised of the Physical Functioning Scale, the Role-Physical Scale, the Bodily Pain Scale, and the General Health Scale. The Mental Component Score is comprised of the Vitality Scale, the Social Functioning Scale, the Role-Emotional Scale, and the Mental Health Scale.

Norm-based scores will also be generated for the eight SF-36 scales and the two summary measures. All eight SF-36 scales and the two summary scores will be normalized to have a mean of 50 and a standard deviation of 10 for the 1998 general US population. The advantage of the standardization is that results for one scale can be meaningfully compared with the other scales, and the scores have a direct interpretation in relation to the distribution of scores in the 1998 general US population. Specifically, scores above or below 50 are above or below the average, respectively, for the 1998 general US population. Because the standard deviation is 10 for all 8 scales, each one point difference in scores is equivalent to one-tenth of a standard deviation unit or an effect size of 0.10. See Appendix 14.1, Scoring the SF-36 Version 2, of this SAP for details regarding calculation of these scores.

Change from baseline in the SF-36 Physical Component Summary (PCS) and Mental Component Score (MCS) domains at Weeks 24 and 48 will be computed for each subject. Missing data will not be imputed.

Analysis: Longitudinal changes in the SF-36 at Weeks 24 and 48 will be compared across the two arms using linear mixed models. A repeated measures random effect model with MCS or PCS as the outcome, and treatment, visit week (actual observed week), and their interaction as predictors. Additionally, a quadratic term for visit week may be included in the model, if significant. Random intercepts and slopes will be fit for each subject using an unstructured covariance structure for each treatment group.

Descriptive statistics will be presented for the MCS and PCS and change from baseline in the MCS and PCS for each treatment group and overall by study visit. MCS and PCS and change from baseline in MCS and PCS will be shown graphically by treatment arm. Spaghetti plots and

summary statistics including 25th percentile, mean, median, and 75th percentile will be plotted for each visit by treatment group.

Model estimates and standard errors of the MCS and PCS and change from baseline in the MCS and PCS will be presented at baseline and Weeks 24 and 48, along with the differences between arms. Appropriate contrasts will be used to test the difference (baseline to Week 24 or Week 48) between treatment arms. Mean predicted values from the model will be plotted over time, alongside the actual values for each study visit.

Additional models may be developed to assess the effect of other covariates, as necessary.

